10.1 Extent of exposure

All study medication administration details will be listed by treatment period and subject. The listing will include the date and time of administration of the morning and evening dose, depending on the treatment period, of either PSL and or erythromycin and total daily dose of both medications.

Exposure data will be listed only.

10.2 Adverse events

All AEs will be coded using the MedDRA[®] and characterized as pre-treatment and treatment-emergent according to the intake of the study medication. Adverse events with a start date prior to the first dose of study medication will be defined as pre-treatment AEs. A treatment-emergent AE (TEAE) is defined as any AE with a start date/time on or after the first dose of study medication or any unresolved event already present before administration of study medication that worsens in intensity following exposure to the treatment. Where dates are missing or partially missing, AEs will be assumed to be treatment-emergent, unless there is clear evidence to suggest that the AE started prior to the first dose of study medication. Missing or partially missing dates for AEs will be handled as described in [Section 4.2.4](#).

Adverse events will be attributed to the treatment period in which they start. Thus, all AEs starting after the first intake of PSL through Day 11 (before PSL on Day 12) will be attributed to Treatment Period 1 including the washout period Day 6 through Day 11. Likewise, all AEs starting after PSL on Day 12 until prior to erythromycin on Day 23 will be attributed to Treatment Period 2 including the washout period Day 17 through Day 22. There is no washout period between the Treatment Periods 3a, 3b and 3c. Adverse events with a start date after first dose of erythromycin in Treatment Period 3a until prior to the first dose of either PSL or erythromycin dose in Treatment Period 3b will be attributed to Treatment Period 3a and likewise for 3b and 3c. In Treatment Period 3c any AE starting more than 168 hours post last dose of erythromycin will be attributed to the SFU period.

All AEs will be recorded in the Case Report form (CRF) from the time of informed consent until study completion or termination. All AEs will be coded (see [Section 3.8](#)) and categorized by intensity (mild/moderate/severe) and relationship (related/not related) as judged by the Investigator.

The number and percentage of subjects who experience TEAEs will be summarized by MedDRA SOC, PT, treatment period (Period 1 and Period 2 pooled, Period 3a, Period 3b, Period 3c and EOS/SFU) and treatment within treatment period (see [Section 3.6](#)). Summaries of TEAEs will include the following:

- Incidence of TEAEs (overview including number and percentage of subjects with any TEAEs, serious TEAEs, discontinuations due to TEAEs, drug-related TEAEs, severe TEAEs and TEAEs leading to death; event counts will also be included)
- Incidence of TEAEs
- Incidence of serious TEAEs
- Incidence of non-serious TEAEs
- Incidence of TEAEs by relationship
- Incidence of TEAEs by maximum relationship
- Incidence of TEAEs by maximum intensity
- Incidence of fatal TEAEs by relationship
- Incidence of non-serious TEAEs by relationship
- Incidence of serious TEAEs by relationship
- Incidence of non-serious TEAEs above threshold of 5% of subjects in any treatment
- Incidence of non-serious TEAEs above threshold of 5% of subjects in any treatment by relationship

Summary tables will contain counts of subjects, percentages of subjects in parentheses and the number of events where applicable. A subject who has multiple events in the same SOC and PT during a given treatment period will be counted only once in the subject counts for that treatment period but all events will be included.

In summaries including relationship, the following relationships will be summarized: 'Not related', 'Related'. Subjects who experience the same event multiple times will be included in the most related category for tabulations by maximum relationship. Events with missing relationship will be considered as 'Related' but recorded as missing in the listings.

In summaries including intensity, the following intensity categories will be summarized: 'Mild', 'Moderate', 'Severe'. Subjects who experience the same event multiple times will be included in the most severe category for tabulations by maximum intensity. Events with missing intensity will be considered as 'Severe' events for summary purposes but recorded as missing in the listings.

Adverse event summaries will be ordered alphabetically by SOC and decreasing frequency of PT within SOC in the 'PSL+erythromycin' column for tables including event counts. For tables including only number and percentage of subjects, summaries will be ordered alphabetically by SOC and decreasing incidence of PT within SOC in the 'PSL+erythromycin' column.

A listing for all AEs will be presented by subject, treatment period and will include the onset date/time and outcome date/time of the event (including relative days), the AE duration (derived), time to onset (derived), pattern of event, intensity, relationship, action taken and outcome. In addition, the listing will flag AEs that led to discontinuation, TEAEs and SAEs.

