3.6 Treatment assignment and treatment group

All subjects will complete the identical fixed-sequence multiple-dose treatments. Listings will be presented by subject and treatment period (Screening, Treatment Periods 1, 2, 3a, 3b and 3c, and SFU). Summaries will be presented by treatment (PSL, erythromycin, PSL + erythromycin and SFU), unless stated otherwise.

- PSL Treatment Period 1 and 2 (pooled data)
- Erythromycin Treatment Period 3a and 3c (pooled data)

- PSL + Erythromycin Treatment Period 3b
- SFU

Adverse events summaries will be presented by treatment within treatment periods as follows:

- Period 1 and 2: PSL
- Period 3a: Erythromycin (pre-PSL)
- Period 3b: PSL + Erythromycin
- Period 3c: Erythromycin (post-PSL)
- SFU

PK summaries will be presented as follows:

- PSL: Period 1
- PSL: Period 2
- PSL + Erythromycin: Period 3b

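### AE tables compare PSL alone over a pooled 22 days, 12 of them washout, with PSL plus erythromycin over 8 dosing days; no matched window or separate Period 1 and 2 summary is planned

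*SAP*

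**What the plan says.** **Attribution.** Under SAP 10.2 an AE belongs to the period in which it starts. For Period 1, "all AEs starting after the first intake of PSL through Day 11 (before PSL on Day 12) will be attributed to Treatment Period 1". Period 2 runs from PSL on Day 12 until just before erythromycin on Day 23. Both expressly include the washout. Within Period 3, onsets up to the first dose of the next sub-period "will be attributed to Treatment Period 3a and likewise for 3b and 3c". An event starting after the Day 34 morning erythromycin dose therefore falls in the column that SAP 3.6 labels "Period 3c: Erythromycin (post-PSL".

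**Columns.** TEAEs are tabulated by "Period 1 and Period 2 pooled, Period 3a, Period 3b, Period 3c and EOS/SFU". SAP 3.6 has the same grouping, and the AE row of SAP Table 13.1 is marked under the combined Period 1 + 2 column, not under Period 1 or Period 2.

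**Measure.** A participant with repeated events in the same SOC and PT "will be counted only once in the subject counts for that treatment period but all events will be included". In the overview, "event counts will also be included". SAP 10.1 adds: "Exposure data will be listed only". The AE listing "will include the onset date/time and outcome date/time of the event (including relative days", and derived time to onset.

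**Protocol.** Protocol 12.1.2 asks for safety by treatment, with PSL alone as one group. Protocol 12.3.2 asks for TEAEs by treatment period as well as by treatment. SAP 3.9 declares one change to the protocol analyses, on MITRA sampling.

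**The concern.** Safety and tolerability of PSL with and without erythromycin is a secondary objective (Protocol 3.2), and AE and SAE incidence is its variable (Protocol 4.2.1). The TEAE tables are the planned answer.

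The percentage of participants with at least one event rises with the length of the window and with the number of times a drug is started. PSL alone gets more of both. Protocol 2.2 says that AE intensity tends to fall over the first days of dosing, and Protocol 2.3 reports new AEs, mainly headache and sleep disturbance, after stopping PSL. Either pattern could load the PSL-alone column.

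Post-PSL onsets are also split unequally. After the Day 5 and Day 16 doses the whole washout stays in PSL alone. After the Day 33 dose only about the first 24 hours stay with the combination. A real but moderate rise in AEs on the combination could then be hard to see in the tables.

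**Working it through.** **1. Day counts against the plan's own figure.**
- Period 1 is Days 1-11 (11 days) and Period 2 is Days 12-22 (11 days), so the pooled window is 22 days.
- Dosing days: 5 + 5 = 10. Washout days (6-11 and 17-22): 6 + 6 = 12. PSL starts: 2.
- Period 3b is Days 26-33: 8 dosing days, one start, no washout.
- PSL days in total: 5 + 5 + 8 = 18, the maximum exposure stated in Protocol 5.4 and SAP 2.3.
- PSL doses: 9 in Period 1, 9 in Period 2, 15 in Period 3b.

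**2. Model (assumed; the documents give no AE rates or timing).** The hazard is h per dosing day and w × h per washout day, and the daily-rate ratio on the combination is HR. Incidence = 1 − exp(−cumulative hazard). PSL alone accumulates h(10 + 12w) and Period 3b accumulates 8 × h × HR. The columns are equal when HR = (10 + 12w)/8:
- w = 0 (dosing days only): 10/8 = 1.25
- w = 0.25: 13/8 = 1.63
- w = 0.5: 16/8 = 2.0
- w = 1 (even spread): 22/8 = 2.75

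If onsets occur only in the first 3 days after a PSL start, PSL alone has 6h and Period 3b has 3h × HR, so the break-even is 2.0. Expected event counts have the same break-evens.

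**3. What a true doubling would look like.** With h = 0.05, 20 participants and independent binomial columns (a simplification):

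| Timing of AEs | PSL alone | Period 3b, HR 2 | Chance 3b is equal or lower |
|---|---|---|---|
| Dosing days only | 39.3% | 55.1% | 0.20 |
| PSL starts | 25.9% | 25.9% | 0.57 |
| Even over all days | 66.7% | 55.1% | 0.82 |

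At h = 0.02 the chances are 0.30, 0.60 and 0.77.

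**4. The same doubling in matched nine-dose windows** (108 h = 4.5 days). At h = 0.05, a constant hazard gives 20.1% against 36.2%, chance 0.17. The starts pattern gives 13.9% against 25.9%, chance 0.22. At h = 0.02 the chances are 0.30 and 0.37. If AEs arise only on dosing days, matching therefore moves the chance from 0.20 to 0.17, or leaves it at 0.30. Under the starts pattern it moves from 0.57 to 0.22, or from 0.60 to 0.37.

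**5. A larger effect.** Suppose the AE hazard rose by 3.2, the AUC ratio in the sample-size section. At h = 0.05 the expected percentages are then 39.3% against 72.2%, 25.9% against 38.1%, and 66.7% against 72.2%. Period 3b is higher under every pattern, and the chance that it looks equal or lower is 0.02, 0.25 and 0.42.

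**6. The opposing force.** An erythromycin AE hazard of 0.25h over Period 3b adds 8 × 0.25h = 2h. The break-evens fall to (10 − 2)/8 = 1.0, (6 − 2)/3 = 1.33 and (22 − 2)/8 = 2.5.

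**7. Separating Periods 1 and 2 is not enough.** One period against 3b has break-even (5 + 6w)/8, from 0.63 (w = 0) to 1.38 (w = 1).

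**The case against.** A reader might infer that pooling Periods 1 and 2 breaches the protocol. It does not: Protocol 12.1.2 asks for PSL alone as one treatment group. What is undeclared is the missing by-period summary. Nor does the sentence in SAP 10 against pooling categorical variables decide the matter, because SAP 3.6, SAP 10.2 and the AE row of Table 13.1 specifically set the AE columns.

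A reader might also infer that the tables will hide a doubling of AEs. The documents do not support that, for these reasons:
- **Even spread is unlikely.** Protocol 2.3 calls post-discontinuation AEs mild and transient. Ascertainment is also lighter in washout: participants may go home on Day 7 or 18, with one visit and telephone contact before re-admission on Day 10 or 21. At w = 0.25 and h = 0.05 a doubling shows as 47.8% against 55.1%.
- **The starts figure is an upper value.** The protocol says that intensity falls over the first days, not that onsets cluster there. The 25.9% also treats a participant's two starts as independent. If the same people react both times, the pooled figure falls towards the single-course 13.9%, and the break-even in per-course risk lies between 1.0 and 25.9/13.9 = 1.86.
- **Chance plays a large part.** With 20 participants, matched windows still miss a doubling with probability 0.17 to 0.22 at 5% per day.
- **Other planned output helps.** Relationship and maximum-intensity tables, event counts, and listings with onset times are all in SAP 10.2.

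All of this stands. It limits the size of the point. It does not make the windows comparable, and no planned table puts the two treatments on a common footing.

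**Conclusion.** The point holds in a limited form. The window lengths, the unequal handling of post-PSL onsets and the undeclared omission of Period 1 and Period 2 TEAE summaries follow directly from the text. The direction of the window effect is also clear: it works against showing more AEs on the combination.

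Its size is uncertain. The break-even daily-rate ratio is 1.25 with dosing-day AEs only, up to about 2.0 with AEs clustered at starts, and at most 2.75. The gain from matching is small unless AEs occur at PSL starts or in washout. The net direction of the displayed comparison is not known either, because erythromycin's own AEs fall in Period 3b and that period is always the third PSL course.

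The tables are descriptive. No primary PK result or stopping rule is affected. Severity is minor to should-change.

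**What to change.** Amend SAP 3.6, SAP 10.2 and Table 13.1:

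- **(a) Columns.** Keep the pooled by-treatment column (Protocol 12.1.2). Add separate Period 1 and Period 2 TEAE columns, as Protocol 12.3.2 asks. Footnote the window lengths: 22 days with 10 dosing days, against 8 days.
- **(b) Matched on-treatment windows.** Add one TEAE overview and one SOC/PT summary from the first PSL dose of each course to about 108 h (Days 1-5, 12-16 and 26-30), so that each window holds nine PSL doses. Show the full Days 26-33 beside it. Footnote that the matched window leaves out the last combination days and may understate the combination if exposure is still rising.
- **(c) Post-PSL onsets.** Summarise these separately in one common window, for example 12 h to 144 h after the Day 5, 16 and 33 doses, by preceding PSL treatment. Footnote four limits: the window overlaps the full Days 26-33 column; erythromycin continues to Day 37; participants are outpatients for part of each washout but confined in Period 3c; and Period 3b is always the third PSL course.

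The cost is SAP wording and a few more descriptive tables. AE onset times and dosing times are already collected, so no new data are needed. The price is a longer AE section.

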10.3 Clinical laboratory evaluations

Laboratory data (clinical chemistry, hematology, and urinalysis) and changes from Baseline (if applicable) for numeric variables will be listed by subject, parameter, treatment period and timepoint. Any laboratory measurements that are BLQ or ALQ will be handled as described in [Section 4.2.2](#). Values outside the reference range for numeric variables will be flagged in the listings and in addition, will be listed separately. The reference ranges will also be reported in the listings.

A separate listing will present the subjects who meet one or more of the following criteria at any treatment period or time point:

- Alanine aminotransferase (ALT) or aspartate aminotransferase (AST) increase ≥ 3 x upper limit of normal (ULN)
- Alkaline phosphatase ≥ 2 xULN
- Total bilirubin increase ≥ 2 xULN

The listing will display only treatment periods and time points for which at least one of the above criteria was fulfilled for a given subject, and will display all results obtained at that treatment period or time point for the specified variables.

A summary of subjects who meet the criteria for potential drug-induced liver injury (PDILI) will be presented together with any additional relevant data collected, if applicable.

Clinical chemistry and hematology parameters will be summarized by treatment period and timepoint for both absolute values and changes from Baseline.

Laboratory variables will be grouped according to the laboratory function panel ([Table 10.1](#)) and categorized as normal, high or low, if applicable, based on the reference range supplied by the analytical laboratory. For selected variables that are identified in [Table 10.1](#) the change in category from Baseline will be presented in shift tables at all post-Baseline timepoints.

Any additional laboratory variables not included in the outputs described previously will be listed separately. These will include the following:

- Serology
- Alcohol and cotinine drug screening, alcohol breath test
- Serum pregnancy test

Figures of mean and mean change from Baseline may be presented for selected laboratory variables that will be identified at the DEM. Figures will be presented with all treatment periods overlaid on the same plot.

Table 10.1: Laboratory measurements

Laboratory assessment	Parameters
Hematology	Hemoglobin ^a , hematocrit, red blood cell count ^a , mean corpuscular volume, platelets ^a , total white blood cell count, and differential consisting of absolute counts and percentages of the following leukocyte types: neutrophils ^a , lymphocytes ^a , monocytes, eosinophils, and basophils
Biochemistry	Sodium, potassium, calcium, inorganic phosphorous, glucose (fasting, only at Screening), urea ^a , creatinine ^a , total bilirubin (conjugated bilirubin when total bilirubin is outside the reference range), total protein, albumin, ALT ^a , AST ^a , and ALP ^a
Viral serology (only at Screening Visit)	HIV-1/2Ab, HBsAg and HCV-Ab
Pregnancy	Serum pregnancy test
Urinalysis	Specific gravity, pH, glucose (fasting, only at Screening), protein, blood, leukocytes, nitrite, ketones, bilirubin, urobilinogen (with dipstick) If protein, blood, or leukocytes are abnormal (positive), a microscopic examination of the sediment will be performed.
Drug screen	Amphetamines/methamphetamines, benzodiazepines, barbiturates, cocaine, cannabis, methadone, tricyclic antidepressants and opiates

ALP=alkaline phosphatase; ALT=alanine aminotransferase; AST=aspartate aminotransferase; HBsAG=hepatitis B surface antigen; HCV-Ab=hepatitis C antibody; HIV-1/2Ab=human immunodeficiency virus-1/2 antibodies; SFU=Safety Follow-Up

^a Shift tables will be presented for these variables

10.4 Vital signs, physical findings, and other observations related to safety

10.4.1 Vital signs

The following vital signs measurements will be obtained with the subject resting in the supine position for 10 minutes:

- Systolic and diastolic blood pressure
- Pulse rate
- Oral body temperature
- Respiratory rate

A by-subject listing of all vital sign measurements and change from Baseline will be presented by treatment period and timepoint.

Descriptive statistics will be reported for all vital sign measurements. Measured values and changes from Baseline will be summarized by vital signs variables and timepoint for each treatment period.

Figures of mean change from Baseline will be presented for each variable. Figures will be presented with all treatment periods overlaid on the same plot.

The number and percentage of subjects with treatment-emergent markedly abnormal (TEMA)/potentially clinically significant (PCS) vital sign values as calculated by the criteria outlined in [Table 10–2](#) will be summarized by treatment period at each timepoint and overall.

Table 10–2: TEMA/PCS criteria for vital signs

Variable	Unit	Low ^a	High ^a
Systolic blood pressure	mmHg	Value <90 and ≥20 decrease from Baseline	Value >140 and ≥20 increase from Baseline
Diastolic blood pressure	mmHg	Value <50 and ≥15 decrease from Baseline	Value >90 and ≥15 increase from Baseline
Pulse rate	bpm	Value <45 and ≥15 decrease from Baseline	Value >90 and ≥15 increase from Baseline

bpm=beats per minute; PCS=potentially clinically significant; TEMA=treatment-emergent markedly abnormal.

^a Both conditions must be satisfied for a measurement to be considered potentially clinically significant.

10.4.2 Electrocardiograms

12-lead ECG will be recorded 3 times at each time point. The individual mean at each time point will be calculated as raw parameters for descriptive analysis. The individual mean and change from baseline (time-matched Baseline day of each treatment period, when applicable) will be summarized using descriptive statistics by treatment period at each time point.

All standard 12-lead ECG recordings will be taken in triplicate with the subject resting in the supine position for at least 10 minutes. The following ECG parameters will be reported:

- PR interval
- QT interval
- QRS interval
- RR interval
- QTc interval (QT corrected for heart rate using Fridericia’s formula [QTcF])
- Heart rate

If available in the database, the QT corrected for heart rate using Bazett’s formula (QTcB) will also be included in the listings and tabulations.

The individual measurements and the mean of the triplicate measurements will be reported in the by-subject listings. The listing will also include the change from Baseline (time-matched Baseline day of each treatment period, when applicable), based on the mean of the triplicate measurements at each timepoint, and will be presented by treatment period and timepoint.

Measured values and changes from time-matched Baseline will be summarized by treatment period and at each timepoint and by ECG variable (based on the mean of the triplicate values at each timepoint). The summaries will include the 2-sided 95% CIs. Mean change from time-matched Baseline in QTcF will be summarized and plotted over time. Figures will be presented with all treatment periods overlaid on the same plot.

The following cut-points in QTcF (observed data and change from time-matched Baseline), based on the mean of the triplicate data, will be summarized categorically (number and percentage of subjects) by treatment period at each timepoint.

For observed data:

- <450msec
- ≥450 to <480msec
- ≥480 to <500msec
- ≥500msec

Absolute change from Baseline in QTcF:

- <30msec
- ≥30 to <60msec
- ≥60 msec

All ECG findings for the individual triplicate measurements will be listed separately.

Any incomplete triplicate measurements at a given timepoint will be handled as described in [Section 4.2.3](#).

10.4.3 Other safety variables

10.4.3.1 Physical examination

Subjects with abnormalities in the physical examination will be listed including details of the abnormality.

10.4.3.2 Columbia-Suicide Severity Rating Scale

Columbia-Suicide Severity Rating Scale (C-SSRS; Posner et al, 2011) data will be listed. Module of the questionnaire, time point, question and the associated response will be listed for all the visits days where this questionnaire is collected.

11 OTHER ANALYSES

A listing of comments will be presented.

13 APPENDICES

13.1 Breakdown of treatment periods reported into the TFLs by study assessment data

Table 13.1: Breakdown of treatment periods reported into the TFLs by study assessment data

Treatment	PSL		PSL	Erythromycin pre	PSL + Erythromycin	Erythromycin post	EOS/SFU	All subjects
	Period 1	Period 2	Period 1 + 2	Period 3a	Period 3b	Period 3c		
Subject disposition	X	X		X	X	X	X	
Protocol deviations	X	X		X	X	X	X	
Demographics								X
Medical history								X
Lifestyle								X
Prior/concomitant medications								X
Adverse Events			X	X	X	X	X	
Laboratory tests	X	X			X	X	X	
Other safety continuous measurements (vital signs, ECG)	X	X		X	X	X	X	
Safety categorical results (laboratory shift tables, PDILI)	X	X			X	X		
PK plasma and urine for PSL and metabolites	X	X			X			

ECG=electrocardiogram; EOS=end of study; PK=pharmacokinetic; PSL=Padsevonil; SFU=Safety Follow-up.

Note: Period refers to the treatment period.

14 **AMENDMENT(S) TO THE STATISTICAL ANALYSIS PLAN**

Not Applicable

This document cannot be used to support any marketing authorization application and any extensions or variations thereof.

REDACTED COPY

STATISTICAL ANALYSIS PLAN SIGNATURE PAGE

This document has been reviewed and approved per the Review and Approval of Clinical Documents Standard Operating Procedures. Signatures indicate that the final version of the SAP or amended SAP is released for execution.

This document cannot be used to support any marketing authorization application and any extensions or variations thereof.

REDACTED COPY

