- i Prior and concomitant medications will be recorded prior to morning dosing.
- j Vital signs (including systolic and diastolic BP, pulse rate, respiration rate, and oral temperature) will be performed at Screening, when study participants are admitted to the unit (D-2, D10, and D21), before each morning dose of PSL and/or erythromycin throughout each treatment period, on D38, and at EOS.
- k In addition to the Screening Visit, a serum pregnancy test (for women of childbearing potential only) and drug screen will be administered when study participants are admitted to the unit (D-2, D10, and D21). Additional serum pregnancy tests (for women of childbearing potential only) will be administered on D37 and at the SFU Visit.
- l A telephone contact to verify any AE or concomitant treatment will occur on D9 and D20.
- m Laboratory safety (hematology, chemistry, and urinalysis) will be performed after a fasting period of at least 4h only at Screening. Laboratory safety (non-fasting) will be performed prior to admission to the unit during each treatment period (D-1, D10, and D21), and prior to morning dosing on D4 during Treatment Period 1, on D15 during Treatment Period 2, and on D26, D30, D33, and D37 during Treatment Period 3, and at EOS.
- n Genotype sample collection for potential exploratory analysis to be collected at predose on D1. Biomarker sample collection for potential exploratory analysis to be collected at predose on D1 and D12 and at 48h postdose on D1 and D12 (i.e., D3 and D14), as well as at 2h postdose on D5 and D16.

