##### **8.4.1 Treatment Period 3a (Day 23 to Day 25)**

Study participants will receive erythromycin 500mg bid administered in the morning and in the evening.

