#### **8.4.2.1 Day 26**

The following procedures/assessments will be performed:

- C-SSRS prior to morning dosing
- Abbreviated physical exam prior to morning dosing
- Prior and concomitant medications recorded prior to morning dosing
- Vital signs (including systolic and diastolic BP, pulse rate, respiration rate, and oral temperature) prior to morning dosing
- Blood and urine samples for the following clinical laboratory tests will be collected prior to morning dosing:
  - Hematology, serum chemistry, and urinalysis
- Blood samples (venous and MITRA) for PK analysis (relative to morning dosing)
  - Predose
  - Postdose: 0.25h, 0.5h, 0.75h, 1h, 1.25h, 1.5h, 2h, 3h, 4h, 6h, 8h, and 12h
- Urine samples for PK analysis (relative to morning dosing)
  - Predose ( $\leq 1$ h before dosing)
  - Postdose: 0 to 12h
- Triplicate 12-lead ECGs
  - Morning dose: Predose, 1h, 2h, 3h and 6h postdose
  - Evening dose: approximately 0.5h predose
- Recording of AEs/medical procedures

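### SAP Table 13.1 leaves end-of-study values out of the laboratory shift/PDILI tables and heads the pre-combination Day 26 laboratory sample as PSL + erythromycin

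*SAP*

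**What the plan says.** **Table 13.1.** SAP 13.1 has columns for Period 1, Period 2, Periods 1 + 2, Period 3a, Period 3b (headed PSL + Erythromycin), Period 3c, EOS/SFU and all subjects. The row "Laboratory tests" is marked for Periods 1, 2, 3b, 3c and EOS/SFU. The row "Safety categorical results (laboratory shift tables, PDILI" is marked for Periods 1, 2, 3b and 3c. Period 3a is blank in both rows, and EOS/SFU is blank in the second.

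**Text on shift tables.** SAP 10.3 says that, for selected variables, the change in category from baseline "will be presented in shift tables at all post-Baseline timepoints". Protocol 12.3.2 makes the same promise for each time point after baseline.

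**Sampling.** Protocol Table 5-1, footnote m, schedules laboratory safety tests at check-in (Days 10 and 21), on Days 4 and 15, and "on D26, D30, D33, and D37 during Treatment Period 3, and at EOS". For Day 26, Protocol 8.4.2.1 says: "Blood and urine samples for the following clinical laboratory tests will be collected prior to morning dosing". That section sits under Treatment Period 3b. For Days 23 to 25, Protocol 8.4.1 says: "Study participants will receive erythromycin 500mg bid administered in the morning and in the evening". No laboratory sample is scheduled on those three days.

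**Period rule for adverse events.** SAP 10.2 says that an event starting after the first erythromycin dose in 3a "until prior to the first dose of either PSL or erythromycin dose in Treatment Period 3b will be attributed to Treatment Period 3a", and that the same logic applies to 3b and 3c. The SAP has no corresponding rule for laboratory values.

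**The concern.** Two separate things are at issue.

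First, SAP Section 10 sends the programmer to Table 13.1 for the layout of safety outputs. A programmer who follows the blank EOS/SFU cell omits a tabulation that the SAP text and the protocol both promise. SAP 3.9, which records changes from the protocol's analyses, does not mention this one. Early withdrawals add to the gap. SAP 4.3 assigns their withdrawal-visit measurements to EOS and keeps other unscheduled or repeated values after the first dose out of descriptive statistics, so their final liver values land in the unmarked column.

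Second, the Day 26 predose sample shows the effect of erythromycin before PSL is added, yet the only marked column it can fall in is the combination column. Protocol 10.2.1 requires every PDILI event to be reported as an adverse event as well. One ALT or AST finding on Day 26 before dosing could therefore be an adverse event under erythromycin alone and a PDILI case under PSL + erythromycin. Safety with and without erythromycin is a secondary objective, so the heading matters for interpretation.

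**Working it through.** There is no sample-size or error-rate figure to reproduce. The check maps each scheduled post-baseline laboratory time point (Protocol Table 5-1, footnote m) to the marked cells of SAP Table 13.1.

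| Time point | Column under the table and visit layout | In laboratory summaries | In shift/PDILI tables |
|---|---|---|---|
| Day 4, Day 10 | Period 1 | yes | yes |
| Day 15, Day 21 | Period 2 | yes | yes |
| Day 26 (predose) | Period 3b | yes | yes |
| Day 30, Day 33 | Period 3b | yes | yes |
| Day 37 (predose) | Period 3c | yes | yes |
| EOS (Day 44 to 47) | EOS/SFU | yes | no |

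**Count.** 2 + 2 + 1 + 2 + 1 + 1 = 9 time points. The laboratory summaries cover 9 of 9. The shift/PDILI tables cover 8 of 9; EOS is the one missing.

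**What EOS adds.**
- Without it, the last categorical time point is Day 37 predose. That is 37 − 33 = 4 days after the last PSL dose and before the two erythromycin doses of Day 37.
- EOS falls 44 − 33 = 11 to 47 − 33 = 14 days after the last PSL dose, and 44 − 37 = 7 to 47 − 37 = 10 days after the last erythromycin dose.

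**What Day 26 predose represents.**
- Erythromycin doses already taken: 3 days × 2 = 6.
- Time since the last PSL dose (morning of Day 16): 26 − 16 = 10 days.
- Coadministered doses taken: 0.
- So 1 of the 3 time points in the Period 3b column (Days 26, 30, 33) precedes the treatment named in its heading.

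**The two rules side by side.** An adverse event that starts before the morning dose on Day 26 belongs to 3a under SAP 10.2. A laboratory value at the same moment cannot be shown in 3a, because that cell is blank in both rows. SAP Section 10 says that categorical variables follow the actual period without pooling, so the period label decides where a PDILI case is counted.

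**After the fix.** Period 1 = Days 4, 10; Period 2 = Days 15, 21; 3a = Day 26; 3b = Days 30, 33; 3c = Day 37; EOS = 1. All 9 time points are in the categorical tables, and 0 of the 2 time points in 3b precede coadministration.

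**The case against.** The strongest case against is that little is hidden and nothing is lost.

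- **Late liver changes.** A reader might infer that liver changes first seen at EOS disappear. They do not. EOS/SFU is marked for the laboratory summaries. SAP 10.3 lists all laboratory data and out-of-range values, and it lists separately every subject who reaches 3xULN for ALT or AST, or 2xULN for ALP or bilirubin, whatever the time point. Its PDILI summary carries no time limit in the text, and a PDILI event would also appear in the adverse event tables, where EOS/SFU is marked. Only the categorical tabulation omits EOS, and only if the table overrides SAP 10.3. Total bilirubin is not flagged for shift tables in SAP Table 10.1 in any case.
- **Blank 3a cells.** They match the schedule, which has no draw on Days 23 to 25, and labelling by scheduled visit is ordinary practice. Both columns exist; the cells are blank. That Day 26 counts as 3b is inferred from the table and visit layout, since no laboratory rule is stated.
- **Dilution of the combination data.** Laboratory outputs are by period and time point, so Day 26 keeps its own row. The heading can mislead mainly in a by-period count such as the PDILI summary.
- **No erythromycin-alone comparator.** A reader might infer this too. It goes too far: Day 37 is taken in erythromycin-only Period 3c, which is marked in both rows. It is an imperfect comparator because it follows eight days that included PSL.
- **Adding the two effects.** It is tempting to say that 2 of 9 samples are misplaced or lost. That sum mixes an omitted tabulation with a heading; no value is lost.

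These points limit the consequence. They do not remove the contradiction between Table 13.1 and SAP 10.3 and Protocol 12.3.2, or the mismatch with the adverse event rule.

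**Conclusion.** The point holds in limited form. Followed as marked, Table 13.1 omits 1 of 9 scheduled post-baseline laboratory time points, and the EOS-mapped values of early withdrawals, from categorical tables that the SAP text and the protocol promise. It also heads 1 of the 3 samples in Period 3b with a treatment not yet given, so a by-period PDILI count could attribute a pre-combination finding to the combination.

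This rests on two assumptions: that the programmer follows Table 13.1 where it conflicts with SAP 10.3, and that Day 26 is labelled by its scheduled visit. The effect is confined to secondary safety displays. The primary PK analysis is untouched. It is still worth correcting before database lock, because the correction needs no new data.

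**What to change.** 1. In Table 13.1, mark EOS/SFU in the shift-table/PDILI row.
2. Mark Period 3a in both laboratory rows and state in SAP 10.3 that the Day 26 predose laboratory sample is assigned to 3a, in line with SAP 10.2.
3. If the rule is extended to the vital-sign TEMA/PCS counts, which SAP 10.4.1 also gives overall by period, apply it to predose values on the first day of each later Period 3 sub-period: Day 26 to 3a and Day 34 to 3b. Day 23 predose is already the Period 3 vital-sign baseline in SAP Table 3-1. No laboratory sample is scheduled on Day 34, so items 1 and 2 do not depend on this.
4. Reconcile SAP 3.6 and Section 10, which pool 3a with 3c, with Table 13.1, which shows them separately. Section 10 averages continuous values across pooled periods. Once Day 26 sits in 3a, that text could blend it with Day 37, which follows PSL exposure.

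Cost: SAP wording and minor re-mapping in the programs. The 3b laboratory column keeps two time points instead of three; the one it gives up precedes the combination.
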